2 ETHICAL CONSIDERATIONS

2.1 Good Clinical Practice

This study will be conducted in full conformance with the International Conference on Harmonisation (ICH) E6 guideline for Good Clinical Practice and the principles of the Declaration of Helsinki or the laws and regulations of the country in which the research is conducted, whichever affords the greater protection to the individual. The study will comply with the requirements of the ICH E2A guideline (Clinical Safety Data Management: Definitions and Standards for Expedited Reporting) and with the E.U. Clinical Trial Directive (2001/20/EC).

The study will be conducted in compliance with the protocol. The protocol and any amendments and the subject informed consent will receive Institutional Review Board/Independent Ethics Committee (IRB/IEC) approval/favorable opinion prior to initiation of the study. All potential serious breaches must be reported to the Sponsor immediately. A serious breach is a breach of the conditions and principles of GCP in connection with the study or the protocol, which is likely to affect, to a significant degree, the safety or physical or mental integrity of the subjects of the study or the scientific value of the study.

Personnel involved in conducting this study will be qualified by education, training, and experience to perform their respective tasks.

This study will not use the services of study personnel where sanctions have been invoked or where there has been scientific misconduct or fraud (e.g., loss of medical licensure, debarment).

2.2 Institutional Review Board/Independent Ethics Committee

This protocol, the Informed Consent Forms, any information to be given to the patient, and relevantsupporting information must be submitted to the IRB/EC by the Principal Investigator and reviewed and approved by the IRB/EC before the study is initiated. In addition, any patient recruitment materials must be approved by the IRB/EC. The investigator should also provide the IRB/IEC with a copy of the Investigator Brochure or product labelling information to be provided to subjects and any updates.

Investigators are responsible for promptly informing the IRB/EC of any protocol amendments (see Section 11.4). In addition to the requirements for reporting all adverse events to the Sponsor, investigators must comply with requirements for reporting serious adverse events to the local health authority and IRB/EC.

2.3 Informed Consent

The Sponsor's sample Informed Consent Form will be provided to each site. Each Site can modify the template provided, but the Sponsor must review and approve any proposed deviations from the sample Informed Consent Forms or any alternate consent forms proposed by the site (collectively, the "Consent Forms") before IRB/EC submission. The final IRB/EC-approved Consent Forms must be provided to the Sponsor for health authority submission purposes according to local requirements.

Regarding specific Informed Consent(s) on optional tumor biopsies, the investigator or authorized designee will explain to each patient the objectives of the exploratory research. Patients will be told that they are free to refuse to participate and may withdraw their specimens at any time and for any reason.

Investigators must ensure that subjects are clearly and fully informed about the purpose, potential risks, and other critical issues regarding clinical studies in which they volunteer to participate. In situations where consent cannot be given to subjects, their legally acceptable representatives are clearly and fully informed about the purpose, potential risks, and other critical issues regarding clinical studies in which the subject volunteers to participate. The language of the consent must be non-technical and easily understood. Investigators should allow time necessary for subject or subject's legally acceptable representative to inquire about the details of the study. The Consent Forms must be signed and dated by the patient or the patient's legally authorized representative before his or her participation in the study. The case history or clinical records for each patient shall document the informed consent process and that written informed consent was obtained prior to participation in the study. A copy of each signed Consent Form must be provided to the patient or the patient's legally authorized representative. All signed and dated Consent Forms must remain in each patient's study file or in the site file and must be available for verification by study monitors at any time. If informed consent is initially given by a subject's legally acceptable representative or legal guardian, and the subject subsequently becomes capable of making and communicating his or her informed consent during the study, consent must additionally be obtained from the subject.

The Consent Forms should be revised whenever there are changes to study procedures or when new information becomes available that may affect the willingness of the patient to participate. The final revised IRB/EC-approved Consent Forms must be provided to the Sponsor for health authority submission purposes.

Patients must be re-consented to the most current version of the Consent Forms (or to a significant new information/findings addendum in accordance with applicable laws and IRB/EC policy) during their participation in the study. For any updated or revised Consent Forms, the case history or clinical records for each patient shall document the informed consent process and that written informed consent was obtained using the updated/revised Consent Forms for continued participation in the study.

2.4 Confidentiality

The Sponsor maintains confidentiality standards by coding each patient enrolled in the study through assignment of a unique patient identification number. This means that patient names are not included in data sets that are transmitted to any Sponsor location.

Patient medical information obtained by this study is confidential and may only be disclosed to third parties as permitted by the Informed Consent Form (or separate authorization for use and disclosure of personal health information) signed by the patient, unless permitted or required by law. Medical information may be given to a patient's personal physician or other appropriate medical personnel responsible for the patient's welfare, for treatment purposes. Data generated by this study must be available for inspection upon request by representatives of the national and local health authorities, Sponsor's monitors, representatives, and collaborators, and the IRB/EC for each study site, as appropriate.

2.5 Financial Disclosure

Investigators will provide the Sponsor with sufficient, accurate financial information in accordance with local regulations to allow the Sponsor to submit complete and accurate financial certification or disclosure statements to the appropriate health authorities. Investigators are responsible for providing information on financial interests during the course of the study and for 1 year after completion of the study (i.e., last patient, last visit).

 - ➤ IPI: 1 mg/Kg i.v. every 8 weeks.
 - TMZ: 150 mg/sqm daily on days 1-5, every 4 weeks.

Treatment will continue until confirmed disease progression, unacceptable toxicity, withdrawal of consent or death, whichever occurs first.

- In case of unacceptable toxicity unequivocally due to TMZ, NIVO and IPI can be continued until disease progression, or to unacceptable toxicity, informed consent withdrawal or death.
- In case of unacceptable toxicity unequivocally due to NIVO and/or IPI, single-agent TMZ can be continued until disease progression, or to unacceptable toxicity, informed consent withdrawal or death.

In the second treatment phase, patients will undergo tumor assessment at baseline and every 8 +/- 1 weeks for the first 12 months following Cycle 1, Day 1. After 12 months, patients will undergo tumor assessments every 12 weeks until confirmed disease progression, unacceptable toxicity, withdrawal of consent or death, whichever occurs first.

Patients entering the second treatment phase can continue treatment after the first occurrence of unequivocal radiographic progression per RECIST v1.1, and until the criteria for progression according to ir-RECIST are met. After discussion with the Sponsor, patients will be permitted to continue study treatment after ir-RECIST criteria for progressive disease are met if they meet all of the following criteria:

- Evidence of clinical benefit (defined as the stabilization or improvement of disease-related symptoms) as assessed by the investigator
- Tolerance of study treatment
- Absence of symptoms and signs (including worsening of laboratory values; [e.g., new or worsening hypercalcemia]) indicating unequivocal progression of disease, despite a rising carcinoembryonic antigen (CEA) level
- No decline in ECOG performance status that can be attributed to disease progression
- Absence of tumor progression at critical anatomical sites (e.g., leptomeningeal disease) that cannot be managed by protocol—allowed medical interventions
- Patients must provide written consent to acknowledge deferring these treatment options in favor of
 continuing study treatment at the time of ir-RECIST defined disease progression. All other elements
 of the main consent including description of reasonably foreseeable risks or discomforts, orother
 alternative treatment options will still apply.
- Sponsor approval

Patients who discontinue from study treatment for reasons other than disease progression (e.g., toxicity) will continue scheduled tumor assessments until disease progression, withdrawal of consent or death, whichever comes first. Patients who start a new anti-cancer therapy in the absence of disease progression should be followed according to the protocol schedule until there is confirmed disease progression, withdrawal of consent or death, whichever occurs first.

CD-ROM copies of the CT scans performed at baseline and during treatment until disease progression according to RECIST v1.1 and ir-RECIST criteria will be collected at the Coordinating Center (s.c. Oncologia Medica 1, Fondazione IRCCS Istituto Nazionale dei Tumori) for central review.

The sample of archived tumor tissues used for molecular screening, as well as blood and plasma samples, will be collected for exploratory biomarker assessments.

Patients will undergo an optional tumor biopsy sample collection, if clinically feasible as assessed by investigators, prior to C3D1 of the second treatment phase and/or at the evidence of radiographic disease progression causing treatment discontinuation. These data will be analyzed for the association between changes in tumor tissue and clinical outcome and to understand further the potential mechanisms of resistance to study treatment. A separate informed consent will be signed for optional biopsies requested by the study.

Longitudinal plasma samples (liquid biopsy and PBMCs) will be collected at baseline and every 4-week until best response according to ir-RECIST; after that, these samples (liquid biopsy and PBMCs) will be collected every 8 +/-1 weeks for the first 12 months and every 12 weeks thereafter and at disease progressionleading to treatment discontinuation.

Safety assessments will include the incidence, nature, and severity of adverse events, changes in vital signs and laboratory abnormalities graded per National Cancer Institute Common Terminology Criteria for Adverse Events (NCI CTCAE), Version 4.0.

Quality of life will be assessed through Patient reported outcomes instruments (PRO) distributed by the study staff and completed in their entirety by the patient. PRO questionnaires should be completed every 8 weeks \pm 7 days during treatment until PD, regardless of whether study treatment has been administered or held, and also if the patient is off treatment due to reason other than PD (i.e. refusal or unacceptable toxicity). After 12 months of treatment, PRO questionnaires will be completed every 12 weeks.

Post-progression, all patients will be followed for survival and subsequent anti-cancer therapy approximately every 3 months until death, loss to follow-up or withdrawal of consent, whichever occurs first.

3.1.2 Treatment beyond progression

Treatment beyond investigator-assessed RECIST 1.1-defined progression will be permitted if the subject experiences investigator-assessed clinical benefit and the subject is tolerating the study treatment (See Section 5.4).

3.1.3 Follow up

Follow-up begins when the decision to discontinue a subject from study therapy is made (no furthertreatment with study therapy).

- Subjects who discontinue treatment for reasons other than tumor progression will continue to have scheduled tumor imaging assessments (every 8 weeks +/- 1 week for the first 12 months following C1D1 and every 12 weeks thereafter) until the patient dies, experiences disease progression (investigator-assessed RECIST 1.1-defined progression), withdraws consent or until the study closes, whichever occurs first. Subjects who started a new anti-cancer therapy in the absence of disease progression should continue to be followed for progression according to the protocol schedule of response assessments unless consent is withdrawn or the patient experiences disease progression or death or until study termination, whichever occurs first.
- All adverse events will be recorded until 30 days after the last dose of study treatment, and SAEs and AESIs will be recorded until 90 days after last dose of study treatment. Ongoing adverse events thought to be related to study treatment will be followed until the event has resolved to baseline grade, the event is assessed by the investigator as stable, new anti-cancer treatment is initiated, the patient is lost to follow-up, the patient withdraws consent, or it has been determined that study treatment or participation is not the cause of the adverse event.
- Following early discontinuation or completion of the treatment period, all patients will be followed for survival and subsequent anti-cancer therapy beginning 3 months after the end of treatment visit. Survival and subsequent anti-cancer therapy follow-up information will be collected via telephone calls, patient medical records, and/or clinic visits approximately every 3 months until death, loss to follow-up, withdrawal of consent, or study termination by the Sponsor.

3.2 End of Study

The end of study is defined as the date of the last follow-up visit of the last patient enrolled and is expected to occur approximately 12 months after the last patient enrolls in the study. Follow-up for survival will continue until all patients have died or are lost to follow-up or the Sponsor decides to end the trial, whicheveroccurs first.

3.3 Data Monitoring Committee (DMC)

A Data Monitoring Committee (DMC) will be used to evaluate safety during the study. Safety data will be reviewed by the DMC on a periodic basis, approximately every 3 months from the date of first-patient-in. In addition, the DMC will review safety data 28 days after the inclusion of the 6th patient. Safety data, including demographics, adverse events, serious adverse events, and relevant laboratory data, will be reviewed.

The DMC will provide a recommendation as to whether the study may continue, whether amendment(s) to the protocol should be implemented, or whether the study should be stopped. The final decision will rest withthe Sponsor.

3.4 Scientific Rationale for study design

The aim of this trial is to evaluate the efficacy and safety of NIVO, IPI and TMZ combination in 27 patients with MSS, MGMT-silenced mCRC with initial clinical benefit following lead-in treatment with single-agent TMZ. The scientific background for this combination and this study design is extensively explained in Section 1.

3.4.1 Rationale for Blood Sampling for Biomarkers

Blood-based non-invasive biomarkers are emerging as an increasingly used tool in clinical practice. Our hypothesis is that we will find a relationship between tumor and plasma biomarkers (including but notlimited to PD-L1, PD-1, methyl-BEAMing, mutational load) and efficacy.

3.4.2 Rationale for the Collection of Tumor Specimens (Archival or Fresh)

An archival specimen, must be submitted as mandatory to the Sponsor. Since published results suggest that expression of PD-L1 in tumors correlates with response to anti-PD-1 therapy, tumor specimens fromenrolled patients will be tested for PD-L1 and PD-1 expression, as well as percentage of MGMT methylation methyl-BEAMing and, in selected cases, mutational burden by whole exome sequencing.

Since prior therapies may have impacted immunohistochemical expression of MGMT, percentage of MGMT methylation (as assessed by quantitative techniques, such as digital PCR methods), and mutational burden, patients may submit specimens obtained after completion of their most recent prior therapy (optional).

In addition to assessment of PD-L1 status, other exploratory markers such as potential predictive and prognostic markers that are related to response or clinical benefit of TMZ, NIVO and IPI treatment, tumor immunobiology, mechanisms of resistance, or tumor type markers, may also be analyzed.

3.4.3 Rationale for the Collection of Tumor Specimens at the Time of Best response/Radiographic Progression

The requirement of a biopsy (if clinically feasible) to be performed at the time of best response, i.e. at C3D1 of the second treatment phase and/or disease progression is not only to confirm progression, but also to explore whether the tumor immune environment (e.g., tumor PD-L1, expression of other immune biomarkers) has changed since the beginning of the TMZ, NIVO and IPI treatment, which may help to investigate possible mechanisms of benefit and resistance to treatment.

3.4.4 Rationale for the Use of Modified Response Criteria (Immune Based)

Cancer immunotherapies may result in early apparent radiographic progression (pseudo progression/tumor immune infiltration), including the appearance of new lesions, followed by delayed response (61). Additionally, responding tumors may appear to increase in size because of the influx of immune cells (62) (63). Unconventional response patterns have been described in patients treated with anti-cytotoxic T lymphocyte—associated antigen 4 (CTLA-4) (61) and have been observed in the preliminary experience with ATEZO in Study PCD4989g. Therefore, ir-RECIST will be used in this study to accommodate the possible appearance of new lesions and to allow the apparent increase in tumor burden to be confirmed at a subsequent assessment prior to designation of progressive disease.

3.4.5 Rationale for Patient-Related Outcomes Assessments

The patient experience of mCRC includes impacts on symptoms (disease and treatment burden), functioning, and HRQoL. Disease-specific symptoms (e.g., bloating, abdominal pain, diarrhea, constipation, loss of appetite) and other symptoms (e.g., fatigue) that negatively impact patients' functioning and quality of life are relevant in this population. Patient-completed questionnaires are included to characterize the impact of

disease and treatment on patients. The collection of this type of data will provide greater insights for both the medical and patient communities to understand disease and treatment burden and resulting HRQoL when patients are exposed to TMZ, NIVO and IPI combination (64).

3.5 Outcome Measures

3.5.1 Efficacy Outcome Measures

The efficacy outcome measures for this study are as follows:

- Investigator-assessed PFS according to RECIST v1.1
- Investigator-assessed PFS according to ir-RECISTThe

secondary efficacy outcome measures are as follows:

- Investigator assessed response rate per RECIST v1.1 or death from any cause on study
- Investigator assessed response rate per ir-RECIST or death from any cause on study
- Investigator assessed DOR per RECIST v1.1
- Investigator assessed DOR per ir-RECIST
- OS
- Centrally-assessed objective response, DOR, PFS according to RECIST vers 1.1 and ir-RECIST

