10 STATISTICAL CONSIDERATIONS

10.1 Sample size determination

This is an open-label, multicenter, single-arm Phase II trial designed to estimate the activity of TMZ in association with NIVO and IPI in MGMT silenced, MSS, advanced CRC patients who have progressed after irinotecan, oxaliplatin, fluoropyrimidines and anti-EGFR mAbs (in *RAS/BRAF* wild type tumors).

According to our previously published results, in MGMT methylated mCRC with initial clinical benefit from TMZ (CR+PR+SD at 8 weeks) the individual PFS is almost always shorter than 6 months, and therefore the median PFS falls between 16- and 24-week reassessments. Therefore, after the first 8-week CT scan reassessment, by adding NIVO and IPI to TMZ, we plan to increase the 8-month PFS rate estimated by the Kaplan-Meier Method from 5% to 20%, with an alfa-error of 0.05 and a beta-error of 0.20.

According to the Fleming single-stage design and selecting the design parameters p0 (8-months PFS rate in the null hypothesis) = 0.05*, and p1 (8-months PFS rate in the alternative hypothesis) = 0.20, respectively, a total of 27 patients will be required. Null hypothesis will be rejected if at least 4 patients will be progression-free at the 8-months reassessment.

- *A null hypothesis of 0.05 is based on the consideration that single agent TMZ does not lead to individual PFS times beyond 6 months in the refractory setting.
- **The alternative hypothesis of 0.20 is considered as a potential target of interest for further studies in this setting with the experimental treatment.

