10.2 Efficacy Analyses

10.2.1 Primary Efficacy Endpoint

The primary efficacy endpoint of this study is the 8-month PFS rate, defined as the proportion of patients alive and progression-free at 8 months from enrollment in the first treatment phase.

The primary endpoint will be 8-month (8-m) PFS in the 27 patients starting the second treatment phase. PFS status and date were assessed by the Investigators in each centre; PFS was defined as the interval from the date of enrollment in the first treatment phase to the date of first objective documentation of PD or deathfrom any cause, whichever occurred first; time was censored at the date of last follow up for patients alive and without PD. PFS will be assessed with the Kaplan-Meier method and 10-month estimates will be calculated and median (95% CI) time will be calculated.

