10.2.2 Secondary Efficacy Endpoints

Secondary Efficacy Endpoints include:

- Investigator-assessed ORR per RECIST v1.1
- Investigator-assessed ORR per ir-RECIST (immune-related criteria)
- Investigator-assessed DOR per RECIST v1.1 and ir-RECIST
- Investigator-assessed PFS per RECIST v1.1 and ir-RECIST
- PRO
- Safety

OS was defined as the interval from the date of enrollment in the first treatment phase to the date of death from any cause or censored to the last follow up for patients alive. OS will be assessed with the Kaplan-Meier method and median (95% CI) time will be calculated. ORR was defined as the proportion of patients who achieved an objective response (CR or PR). DoR was defined as the time from the date of first documented response to the date of PD or death from any cause, whichever occurred first; time was censoredat the date of last follow up for patients alive and without PD. DOR will be assessed with the Kaplan-Meier method and median (95% CI) time will be calculated.

10.3 Overall response rate and Duration of Response as Determined by Investigator per RECIST v1.1 and Ir-RECIST

For the first endpoint (ORR), objective response is defined as a confirmed CR or PR as determined by the investigators per RECIST v1.1 (see Appendix III). Patients not meeting these criteria, including patients without at least one post-baseline response assessment, will be considered non-responders. For the second endpoint (ORRmod), ir-RECIST responses, which incorporate measurement of new lesions and confirmation by repeat assessment performed ≥ 28 days after the first criteria for response are first met, are described in detail in Appendix II. For the analysis according to ir-RECIST, patients not meeting these criteria, including patients without at least one post-baseline response assessment, will be considered non-responders.

DOR will be analyzed for the subset of *objective response-evaluable* patients who achieved an objective response as assessed by the investigator per RECIST v1.1 and Ir-RECIST. The DOR is defined as the time from the initial occurrence of documented CR or PR (whichever occurs first) until documented disease progression as determined by the investigator or death due to any cause, whichever occurs first.

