Stable Disease (SD): Neither sufficient shrinkage to qualify for PR nor sufficient increase to qualify for PD, taking as reference the smallest sum of the diameters while on study.

Progressive Disease (PD): At least a 20% increase in the sum of diameters of all target and all new measurable lesions, taking as reference the smallest sum on study (*nadir SlD*; this includes the baseline sumif that is the smallest on study). In addition to the relative increase of 20%, the sum must also demonstrate an absolute increase of at least 5 mm.

Impact of New Lesions on Ir-RECIST

New lesions alone do not qualify as progressive disease. However, their contribution to total tumor burden is included in the sum of the diameters, which is used to determine the overall ir-RECIST tumor response.

EVALUATION OF BEST OVERALL RESPONSE USING IR-RECIST:

TIMEPOINT RESPONSE

It is assumed that at each protocol-specified timepoint, a response assessment occurs. Table 11 provides a summary of the overall response status calculation at each timepoint for patients who have measurable disease at baseline.

MISSING ASSESSMENTS AND NOT EVALUABLE DESIGNATION

When no imaging/measurement is done at all at a particular timepoint, the patient is not evaluable (NE) at that timepoint. If only a subset of lesion measurements are made at an assessment, usually the case is also

considered NE at that timepoint, unless a convincing argument can be made that the contribution of the individual missing lesion(s) would not change the assigned timepoint response. This would be most likely to happen in the case of PD. For example, if a patient had a baseline sum of 50 mm with three measured lesions and at follow-up only two lesions were assessed but those gave a sum of 80 mm, the patient will have achieved PD status, regardless of the contribution of the missing lesion.

Table 11 Ir-RECIST Timepoint Response Definitions

Target Lesion	Non-	New	New	Overall Ir-
Definition	Target	Measurable	Unmeasurable	RECIST
	Lesion	Lesions	Lesions	Timepoint
	Definition			Response
CR	CR	No	No	CR
CR	Non-CR or not	No	No	PR
	all evaluated			
PR	Any	Yes or no	Yes or no	PR
SD	Any	Yes or no	Yes or no	SD
Not evaluated	Any	Yes or no	Yes or no	NE
PD	Any	Yes or no	Yes or no	PD
	•			

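### The primary 8-month PFS rate names no progression criterion, and the protocol carries both RECIST v1.1 and ir-RECIST, which can differ by the one patient who decides success

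*Protocol*

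**What the plan says.** **Primary objective and endpoint.** Section 1.3.1 and the protocol summary give the primary objective as efficacy measured by the 8-month PFS rate, with no criterion for progression. Section 10.2.1 defines the rate and dates the event at "the date of first objective documentation of PD" or death. It names the investigator as assessor but not the criteria to be used.

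**Outcome lists.** Section 3.5.1 and the summary begin with "Investigator-assessed PFS according to RECIST v1.1" and PFS by ir-RECIST, side by side. The list that follows is headed as secondary. Section 10.2.2 places "Investigator-assessed PFS per RECIST v1.1 and ir-RECIST" among the secondary endpoints. Section 10.4 defines PFS by both sets of criteria without giving either precedence.

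**Criteria.** Under Appendix III (RECIST v1.1), a new lesion is progression, and so is unequivocal progression of non-target lesions. Under Appendix II (ir-RECIST), "New lesions alone do not qualify as progressive disease": new measurable lesions are added to the sum of diameters, and non-target lesions play no part in declaring progression. Under section 10.4, ir-RECIST progression that a later scan fails to confirm is not an event.

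**Design.** Section 10.1 sets "p0 (8-months PFS rate in the null hypothesis) = 0.05", an alternative of 0.20 and 27 patients, "with an alfa-error of 0.05 and a beta-error of 0.20". "Null hypothesis will be rejected if at least 4 patients" are progression-free at 8 months. The null is justified by the history of single-agent temozolomide (TMZ).

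**Response outcomes.** Section 3.5.1 and the summary also list "Investigator assessed response rate per RECIST v1.1 or death from any cause on study", with a matching item for ir-RECIST.

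**The concern.** The definition of the primary event is incomplete, and the lists that might complete it disagree on the standing of the two PFS versions. Both readouts will exist for the same patients: section 3.1.1 allows treatment to continue after RECIST v1.1 progression until ir-RECIST progression, so some patients will be scanned past the first event. In an open-label, single-arm trial with investigator assessment, a criterion that can still be settled after the data are seen is a route to bias. Here the alternative criterion moves the result in one direction only. The test also depends on a fixed 5% null, which may not suit a more permissive definition of progression.

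**Working it through.** **1. Reproduce the design.** Inputs from section 10.1: n = 27, p0 = 0.05, p1 = 0.20, success if X ≥ 4. Sidedness is not stated; the rule points one way, so it is read as one-sided.

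P(X ≥ 4 | n, p) = 1 − Σ(k = 0 to 3) C(27, k) p^k (1 − p)^(27 − k)

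- p = 0.05: 1 − (0.2503 + 0.3558 + 0.2434 + 0.1068) = 0.0437.
- p = 0.20: 1 − (0.0024 + 0.0163 + 0.0530 + 0.1105) = 0.818.

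The smallest n with exact type I error at most 0.05 and power at least 0.80 is 27 with a cut-off of 4. The protocol's design is reproduced.

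**2. Direction of the difference between the criteria.** Take one patient and one set of scans.

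| Finding on a scan | RECIST v1.1 (Appendix III) | ir-RECIST (Appendix II, section 10.4) |
|---|---|---|
| Target sum up ≥ 20% and ≥ 5 mm, no new lesion | PD | PD, unless a later scan fails to confirm it |
| New lesion, total sum below the PD threshold | PD | Not PD |
| Unequivocal non-target progression only | PD | Not PD |

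The two sums of diameters are the same until a new measurable lesion appears, and that lesion is already PD under RECIST v1.1. Confirmed ir-RECIST PD is dated back to the scan that first met its criteria, which cannot precede RECIST v1.1 PD. So in each patient the ir-RECIST date is the same or later, and the number progression-free at 8 months by ir-RECIST is equal or higher.

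**3. Effect of one patient.** One patient is 1/27 = 3.7 percentage points. 3/27 = 11.1% fails; 4/27 = 14.8% succeeds. The probability of exactly 3 of 27 is 0.107 at a true rate of 5% and 0.111 at 20%, so a result one patient short of the cut-off is not remote. If success were in effect declared at 3 or more, type I error would be 0.150.

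**4. Sensitivity to the no-benefit rate.** The protocol gives no no-benefit rate under ir-RECIST. The rates below other than 5% are assumptions, for illustration only.

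| True no-benefit rate at 8 months | P(X ≥ 4 of 27) |
|---|---|
| 4% | 0.022 |
| 5% (protocol) | 0.044 |
| 6% | 0.076 |
| 7% | 0.117 |
| 10% | 0.282 |

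The 0.05 level is crossed at about 5.2%.

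**5. Source of the null.** The background cites RECIST for the historical TMZ response rate. Neither the summary nor section 10.1 says which criterion lay behind the historical progression times.

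**6. Response-rate wording.** Section 10.2.2 defines ORR as the proportion with CR or PR. Section 10.3 makes everyone who does not meet the response criteria a non-responder. The item in section 3.5.1 joins response and death, which contradicts both.

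**The case against.** **The text leans towards RECIST v1.1.** It is listed first in section 3.5.1. Section 3.1.3 ends imaging at RECIST 1.1 progression for patients who stopped treatment for other reasons, and the word for first documentation in section 10.2.1 fits a criterion that needs no confirmation. This is fair evidence of intent, but it does not settle the matter, because section 10.4 also dates confirmed ir-RECIST progression to its first occurrence.

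**The secondary list is not in itself a contradiction.** A reader might infer from section 10.2.2 that no PFS measure is left as primary. That goes too far. The primary is a rate at one time point, whereas section 10.4 treats the secondary PFS as a Kaplan-Meier curve with a median. The two can coexist, and section 10.2.2 has no 8-month RECIST item to remove. What stands is that neither list says which criterion the primary rate uses.

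**ir-RECIST does not ignore new lesions.** Appendix II adds up to five new measurable ones to the sum, and they can produce PD. Only the weaker statement holds: a new lesion by itself is not PD.

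**The 5% null may already be generous.** Section 10.1 says that single-agent TMZ does not yield PFS beyond 6 months, and the summary at one point speaks of raising the rate from 0%. If the true RECIST v1.1 rate is below 5%, ir-RECIST would have to use up that margin before type I error passed 0.05; at 4% it is 0.022. Reclassification also needs a scan after RECIST v1.1 progression, which mainly concerns patients treated past it. Both points limit the likely size.

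**Kaplan-Meier.** Section 10.1 says the rate is estimated by that method. The patient-level ordering carries over strictly to the count of 4 in 27, but in unusual censoring patterns a Kaplan-Meier estimate need not follow it.

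**Conclusion.** The point holds. The primary endpoint lacks a progression criterion, no section supplies one, and the outcome lists give two candidates without ranking them for this purpose. That the ir-RECIST count is equal or higher follows from the protocol's own definitions and needs no assumption. The result can turn on a single patient, at 3/27 against 4/27.

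Two further inferences are not supported. The figures 0.076 to 0.282 are not estimates of the trial's type I error: they rest on assumed no-benefit rates of 6% to 10%, and only the crossing point of about 5.2% follows from the rule alone. Nor do the documents establish that the 5% null was derived under RECIST v1.1. They cite RECIST for historical response, not for historical PFS. What can be said is that they give no support for 5% under ir-RECIST.

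The response-or-death wording is a separate drafting error. A reader might fear that deaths would be counted as responses, but sections 10.2.2 and 10.3 define response correctly. The wording should be corrected because it contradicts them.

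**What to change.** - State in the summary and in sections 1.3.1, 3.5.1 and 10.2.1 that the single primary endpoint is the 8-month PFS rate by investigator-assessed RECIST v1.1, and that the first RECIST v1.1 progression is the event even where study treatment continues.
- Label ir-RECIST PFS as secondary throughout. The full RECIST v1.1 PFS curve and its median may stay secondary.
- Delete the reference to death from the two response-rate outcomes in the summary and section 3.5.1.

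The cost is wording only. Both assessments are already planned, and n = 27, the cut-off of 4, type I error 0.044 and power 0.818 are unchanged. If the sponsor preferred ir-RECIST as primary, it would need its own justified null. For example, a null of 6% or 7% would need a cut-off of 5 at n = 27, and power at 20% would fall to 0.652.
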